#### 4.3.7.3 Primary Analysis of Secondary Endpoint

The TL tumour size and percentage change in TL tumour size from baseline is summarised using descriptive statistics and presented at each timepoint for the Safety set. Descriptive statistics for the percentage change from baseline at week 16 are presented, together with the number of subjects with a baseline and at least 1 post-baseline assessment.

The percentage change from baseline in TL tumour size is presented graphically using waterfall plots, with the bars ordered from the largest increase to the largest decrease. Separate waterfall plots are used to present each subject's week 16 percentage change in TL tumour size as a separate bar. A reference line at the -30% change in TL tumour size level is added to the plots, which corresponds with the definition of 'partial response'. All progressions are marked with a '•' or designated with patterns or colours for ORR categories. Flagged progressions on the percentage change in TL tumour size at week 16 are based upon NTL or new lesion progression at that timepoint and flagged progressions on the best percentage change are based upon NTL or new lesion progression at the same timepoint as the best percentage change. The scale in these plots is fixed to be from -100 to 100 to avoid presenting extreme values. Values that are capped as a result of this restriction to the scale are marked with '#'. Values are ordered in descending order with the imputations due to death appearing first followed by a gap followed by all other subjects. These plots will be produced for the Safety Set.

#### 4.3.7.4 Sensitivity Analyses of the Secondary Endpoint

As a sensitivity analysis, percentage change in TL tumour size is analysed in addition as described in 4.3.7.3 but using the investigator assessment per RECIST 1.1.

# 4.3.7.5 Supplementary Analyses of the Secondary Endpoint

Not applicable.

#### 4.3.7.6 Subgroup Analyses

For a detailed description of the Subgroup Analyses, see section 4.3.

# 4.3.8 Secondary Endpoint: Best Percentage Change in target lesion tumour size

Best Percentage Change in target lesion tumour size is a secondary efficacy endpoint.

#### 4.3.8.1 Definition

The TL tumour size and percentage change from baseline in the sum of TL tumour size at each assessment are calculated. The best absolute change in TL tumour size from baseline (i.e. depth of response) is the largest decrease from baseline or the smallest increase from baseline in the absence of reduction and includes all assessments:

- up to and including the first visit at which the overall visit response is PD,
- prior to death in the absence of progression,
- prior to the start of subsequent anti-cancer therapy (excluding radiotherapy);
- or up to and including the last evaluable RECIST assessment if the subject has not died, progressed or started subsequent anti-cancer therapy.

Each post-baseline disease assessment for a subject that meets the following conditions are included: all target lesions identified at baseline have measurements recorded at the current visit (i.e. they cannot be not done or not evaluable). If a lesion is recorded as  $\leq 5$  mm then this will be used in the calculations.

#### 4.3.8.2 Derivations

If best percentage change cannot be calculated due to missing data (including if the patient has no TLs at baseline), a value of +20% will be imputed as the best percentage change from baseline in the following situations (otherwise best percentage change is left as missing):

- If a patient has no post-baseline assessment and has died
- If a patient has new lesions or progression of NTLs or TLs
- If a patient has withdrawn due to PD and has no evaluable TL data before or at PD

#### 4.3.8.3 Handling of Dropouts and Missing Data

If best percentage change cannot be calculated due to missing data (including if the subject has no TLs at baseline), a value of +20% is imputed as the best percentage change from baseline in the following situations (otherwise best percentage change is left as missing):

- If a subject has no post-baseline assessment and has died
- If a subject has new lesions or progression of non-target lesions (NTLs) or TLs
- If a subject has withdrawn due to PD and has no evaluable TL data before or at PD

#### 4.3.8.4 Primary Analysis of Secondary Endpoint

Descriptive statistics for the best percentage change from baseline are presented, together with the number of subjects with a baseline and at least 1 post-baseline assessment.

The best percentage change from baseline in TL tumour size is presented graphically using waterfall plots, with the bars ordered from the largest increase to the largest decrease. Separate waterfall plots are used to present each subject's best percentage change in TL tumour size as a separate bar. A reference line at the -30% change in TL tumour size level is added to the plots, which corresponds with the definition of 'partial response'. All progressions are marked with a '•' or designated with patterns or colours for ORR

categories. Flagged progressions on the best percentage change in TL tumour size at week 16 are based upon NTL or new lesion progression at that timepoint and flagged progressions on the best percentage change are based upon NTL or new lesion progression at the same timepoint as the best percentage change. The scale in these plots is fixed to be from -100 to 100 to avoid presenting extreme values. Values that are capped as a result of this restriction to the scale are marked with '#'. Values are ordered in descending order with the imputations due to death appearing first followed by a gap followed by all other subjects. These plots will be produced for the Safety set.

# 4.3.8.5 Sensitivity Analyses of the Secondary Endpoint

As a sensitivity analysis, best percentage change in TL tumour size is analysed in addition as described in 4.3.7.3 but using the investigator assessment per RECIST 1.1.

# 4.3.8.6 Supplementary Analyses of the Secondary Endpoint

Not applicable.

# 4.3.8.7 Subgroup Analyses

For a detailed description of the Subgroup Analyses, see section 4.3.

# 4.3.9 Secondary Endpoint: Progression Free Survival

PFS is a secondary efficacy endpoint.

#### 4.3.9.1 Definition

PFS is defined as the time from randomisation until the date of first documented disease progression as assessed by BICR or death (by any cause in the absence of disease progression), regardless of whether the subject withdraws from study therapy or receives another anti-cancer therapy prior to progression.

#### 4.3.9.2 Derivations

PFS (months) = (date of PFS event (progression/death) or censoring – date of randomisation + 1) / (365.25/12)

Subjects who have not progressed or died at the time of analysis are censored at the time of the latest date of assessment from their last evaluable disease assessment. However, if the subject progresses or dies immediately after two or more consecutive missed visits, the subject is censored at the time of the latest evaluable disease assessment prior to the two missed visits. (Note: a not evaluable visit is not considered as a missed visit).

For the time period where the 8-weekly schedule applies, two or more consecutive missing visits resulting in  $\ge 18$  weeks after the last evaluable post-baseline disease assessment, allowing for early and late visits (i.e.  $2 \ge 8$  weeks + 1 week for an early assessment + 1 week for a late assessment = 18 weeks).

If the two missed visits occur over the period when the scheduled frequency of RECIST assessments changes from 8-weekly to 12-weekly this equates to 22 weeks (i.e. the average of 8 and 12 weeks which gives 10 weeks and then apply the same rationale, hence  $2 \times 10$  weeks + 1 week for early assessment + 1 week for late assessment = 22 weeks).

When the scheduling changes to 12-weekly assessments, two missing visits equate to 26 weeks (2 x 12 weeks + 1 week for early assessment + 1 week for late assessment = 26 weeks).

If subjects have no evaluable disease assessments post-baseline or do not have baseline tumour assessment data they will be censored at Day 1 unless they die within two visits of baseline (16 weeks plus 1 week allowing for a late assessment within the visit window) when the death date qualifies as a PFS event.

A summary of censoring rules and the date of PD/death or censoring are given in Table 6. Note that censoring overrides event in certain specified cases.

Situation	Date of PD/Death or Censoring	PFS Outcome
Documented PD or death in the absence of progression	Date of earliest documentation of PD or date of death in the absence of progression	Event
Either no tumour assessment at baseline or no evaluable assessments post-baseline AND death prior to second scheduled post-baseline disease assessment	Date of death	Event
Either no tumour assessment at baseline or no evaluable assessments post-baseline AND no death prior to second scheduled post-baseline disease assessment	Date of randomisation	Censored
PD or death (in the absence of progression) immediately after $\geq 2$ consecutive missed disease assessments as per the protocol specified assessment schedule	Last evaluable progression-free disease assessment prior to missed assessments	Censored
On-going with neither PD nor death at the time of analysis or lost to follow-up or withdrawn consent	Date of last evaluable disease assessment	Censored
Initiation of subsequent anticancer treatment prior to PD or death.	Date of the last progression-free disease assessment prior to initiation of subsequent anticancer treatment	Censored for sensitivity analysis only
COVID-19 related deaths	Date of last evaluable RECIST 1.1 assessment prior to COVID-19 infection related to death	Censored for sensitivity analysis only

#### Table 6Summary of Censoring Rules for PFS

PD = progressive disease; PFS = progression-free survival

The PFS time is always derived based on scan/assessment dates not visit dates.

RECIST assessments/scans contributing towards a particular visit may be performed on different dates. The following rules are applied:

- For investigator assessments, the date of progression is determined based on the earliest RECIST assessment/scan dates of the component that indicates progression.
- For BICR assessments, the date of progression is determined based on the earliest dates of the component that triggered the progression on the first set of scans that indicates progression for the adjudicated reviewer selecting disease progression per RECIST 1.1, or of either reviewer where both reviewers select disease progression per RECIST 1.1 as a time point response, and there is no adjudication for central review (BICR) data.
- When censoring a subject for PFS the subject is censored at the latest of the dates contributing to a particular overall visit assessment.

Note: for TLs only the latest scan date is recorded out of all scans performed at that assessment for the TLs and similarly for NTLs only the latest scan date is recorded out of all scans performed at that assessment for the NTLs.

The proportion of subjects alive and progression-free at 3, 6, 9, 12 and 18 months from randomisation is defined as the Kaplan-Meier estimate of PFS (per RECIST 1.1) at these specific months.

Potential duration of follow-up for PFS, applicable only for PFS censored subjects, is defined as follows:

Potential duration of follow-up for PFS in censored subjects (months) = (date of PFS censoring – date of randomisation + 1) / (365.25/12).

#### 4.3.9.3 Handling of Dropouts and Missing Data

See Section 4.3.9.2.

#### 4.3.9.4 Primary Analysis of Secondary Endpoint

The analysis of PFS is based on the Full analysis set. The number and percentage of subjects experiencing a PFS event (broken down by type of event/censoring) are provided along with the median PFS and its two-sided 95% CI estimated using the Kaplan-Meier method. Kaplan-Meier plots of PFS are presented by treatment arm. Moreover, the landmark estimates of PFS at 3, 6, 9, and 12 months from randomisation are summarised by treatment arm.

The treatment status at progression of subjects at the time of analysis are summarised. This includes the number (%) of subjects who were on treatment at the time of progression, the number (%) of subjects who discontinued study treatment prior to progression, the number (%) of subjects who have not progressed and were on treatment or discontinued treatment.

PFS is analysed using a log-rank test stratified by the randomisation stratification factors (baseline LDH and IO resistance). The Hazard Ratio (HR) together with its 95% CI and p-value is presented. The HR and CI are estimated from a stratified Cox proportional hazard model with ties=Efron, and the CI is calculated using a profile likelihood approach.

A summary of 'potential' duration of follow-up for PFS is included using median (range). This is presented for censored subjects (including all types of PFS censoring).

#### 4.3.9.5 Sensitivity Analysis of Secondary Endpoint

As a sensitivity analysis, PFS is analysed also using the investigator assessment per RECIST 1.1.

Another sensitivity analysis for PFS is performed censoring PFS at the date of the last progression-free disease assessment prior to initiation of subsequent anticancer treatment. The rationale for this sensitivity analysis is that it allows to indirectly estimate the impact of initiating a subsequent cancer treatment on the PFS. For example, a subject that is progression-free at the date of the last assessment prior to subsequent anticancer treatment, starts subsequent anticancer treatment and progresses on the following assessment is no longer contributing on the PFS for the whole time period until progression since that subject will be censored prior to that.

A further sensitivity is conducted to assess the potential of impact on COVID-19 related deaths on PFS. That is, the subjects who had a PFS event due to death where the primary or secondary cause of death was COVID-19 infection or COVID-19 infection was reported as a fatal AE, are censored at the last evaluable RECIST 1.1 assessment prior to COVID-19 infection related to death. If less than five events appear and less than 2% of enrolled subjects are affected the sensitivity analysis will not be carried out.

#### 4.3.9.6 Supplementary Analyses of the Secondary Endpoint - Assessment bias

The following summaries of the number of disagreements between investigator and central reviews of RECIST progression will be presented for each treatment group:

- Total number of disagreements
- Number of disagreements within 2 weeks
- Progression date >2 weeks earlier by central review than by investigator (does not include instances where progression by central review but not by investigator)

- Progression date >=2 weeks earlier by investigator than by central review (does not include instances where progression by investigator but not by central review)
- Investigator but not central review
- Central review but not investigator

In addition, the following will also be summarised:

- number or patients where there is no progression for both central review and investigator assessed,
- early discrepancy rate defined as the number of investigator declared progressions before central review as a proportion of all investigator progressions and corresponding difference in rates between treatment groups
- late discrepancy rate defined as the number of investigator declared progressions after central review as a proportion of all discrepancies and corresponding difference in rates between treatment groups

#### 4.3.9.7 Subgroup Analyses

For a detailed description of the Subgroup Analyses, see section 4.3 . The results of subgroup analyses will be presented on a forest plot including the HR and 95% CI, along with the results of the overall analysis.

#### 4.3.10 Secondary Endpoint: Overall Survival

OS is a secondary efficacy endpoint.

#### 4.3.10.1 Definition

OS is defined as the time from the date of randomisation until death due to any cause regardless of whether the subject withdraws from study therapy or receives another anticancer therapy.

#### 4.3.10.2 Derivations

OS (months) = (date of death or censoring – date of randomisation +1) / (365.25/12)

Any subject not known to have died at the time of analysis is censored based on the last recorded date on which the subject was known to be alive.

Note: Survival calls are made in the week following the date of DCO for the analysis, and if subjects are confirmed to be alive or if the death date is post the DCO date these subjects are censored at the date of DCO. The status of ongoing, withdrawn (from the study) and "lost to follow-up" subjects at the time of any formal OS analysis should be obtained by the site personnel by checking the subject's notes, hospital records, contacting the subject's general practitioner and checking publicly-available death registries. In the event that the

subject has actively withdrawn consent to the processing of their personal data, the vital status of the subject can be obtained by site personnel from publicly available resources where it is possible to do so under applicable local laws.

Note: For any other OS analysis performed, in the absence of survival calls being made, it may be necessary to use all relevant CRF fields to determine the last recorded date on which the subject was known to be alive for those subjects still on treatment (since the *SURVIVE* module is only completed for subjects off treatment if a survival sweep is not performed). The last date for each individual subject is defined as the latest among the following dates recorded on the CRFs:

- AE start, stop and change in severity dates
- Admission and discharge dates of hospitalisation
- Study treatment date
- End of treatment date
- Concomitant medication start and stop dates
- Laboratory test dates
- Date of vital signs
- Date of ECGs
- Physical examination dates
- Cardiovascular data
- Disease assessment dates on RECIST CRF
- Start and stop dates of alternative anticancer treatment
- Date last known alive on survival status CRF
- End of study date (excluding patients lost to follow-up)
- Patient Reported Outcomes (PRO) questionnaire dates

The proportion of subjects alive at 6, 9, 12, and 18 months is defined as the Kaplan-Meier estimate of OS at that particular month.

"Potential" duration of follow-up for OS, applicable only for OS censored subjects, is defined as follows:

Potential duration of follow-up for OS (months) = (date of OS censoring [date last known to be alive] – date of randomisation + 1) / (365.25/12).

#### 4.3.10.3 Handling of Dropouts and Missing Data

If a subject is known to have died where only a partial death date is available then the date of death will be imputed as the latest of the last date known to be alive +1 from the database and the death date using the available information provided:

a. For Missing day only – using the  $1^{st}$  of the month.

b. For Missing day and Month – using the 1st of January.

# 4.3.10.4 If death has been recorded but the date is entirely missing, then date of death will be imputed as the date the patient was last known to be alive +1.Primary Analysis of Secondary Endpoint

The analysis of OS is based on the Full analysis set. The number and percentage of subjects experiencing an OS event and Kaplan-Meier plots of OS are presented. Additionally, summaries of the numbers and percentages of subjects who have died, those still in survival follow-up, those lost to follow-up and those who have withdrawn consent are provided. The median OS and two-sided *95*% CI are estimated using the Kaplan-Meier method.

Moreover, the landmark estimates of OS at 6, 9, 12, and 18 months from randomisation are summarised by treatment arm with corresponding 95% CI.

A summary of the potential duration of follow-up for OS is included using median (range). This is presented for censored subjects.

OS is analysed using a log-rank test stratified by the randomisation stratification factors (baseline LDH and IO resistance). The HR together with its 95% CI and p-value is presented. The HR and CI are estimated from a stratified Cox proportional hazard model with ties=Efron, and the CI are calculated using a profile likelihood approach.

#### 4.3.10.5 Sensitivity Analyses of the Secondary Endpoint

A sensitivity analysis is conducted to assess the potential impact of COVID-19 related deaths on OS. That is, subjects who had a death event where the primary or secondary cause was COVID-19 infection or COVID-19 infection was reported as a fatal AE, are censored at the date of their COVID-19 infection related death. If less than five events appear and less than 2% of enrolled subjects are affected the sensitivity analysis will not be carried out.

#### 4.3.10.6 Supplementary Analyses of the Secondary Endpoint

Not applicable

#### 4.3.10.7 Subgroup Analyses

For a detailed description of the Subgroup Analyses, see section 4.3 Subgroup

**Analyses**. The results of subgroup analyses will be presented on a forest plot including the HR and 95% CI, along with the results of the overall analysis.

# 4.3.11 Secondary Endpoint: PK of ceralasertib

PK of ceralasertib alone and when in combination with durvalumab is a secondary endpoint.

See section 4.5

# 4.3.12 Safety Analysis

The domain safety covers exposure, adverse events, clinical laboratory, vital signs, and electrocardiogram (ECG).

Tables are provided for the safety set, listings are provided for all subjects or the safety set depending on the availability of data.

#### 4.3.12.1 Exposure

#### 4.3.12.1.1 Definitions and Derivations

#### **Duration of exposure**

- Duration of exposure to ceralasertib = min(date of last dose where dose > 0 mg +o21, date of death, date of DCO) first dose\* date +o1
- Duration of exposure to durvalumab = min(date of last dose where dose > 0 mg +o20 date of death, date of DCO) - first dose\* date +o1

\*First dose refers to earliest dose of either treatment

#### Actual duration of exposure (weeks)

- Actual exposure to ceralasertib [months] = total exposure to ceralasertib total duration of dose interruptions and dose delays
- Actual exposure to durvalumab [months] = total exposure to durvalumab total duration of dose delays

The total duration of dose delays is defined as any length of time in addition to the planned cycle length where the patient has not taken/received any of the planned doses.

- Definition of dose delay for ceralasertib: if the number of days between Day 1 of a cycle and Day 1 of the previous cycle is > 28 days, then the number of additional days above 28 days is the duration of delay.
- Definition of dose delay for durvalumab: for Cycle 1, if the number of days between the first administration of durvalumab on Day 8 and the first administration of ceralasertib on Day 1 is > 7 days, then the number of additional days above 7 days is the duration of the delay. For all subsequent cycles, if the number of days between Dayo8 of a cycle and Day 8 of the previous cycle is > 28 days, then the number of additional days above 28 days is the duration of delay.

The total duration of dose interruption is defined as any length of time during the cycle where the patient has not taken/received any of the planned doses.

• Definition of dose interruptions for ceralasertib: the total number of full-day treatment interruptions, including missed and forgotten doses. Half-day interruptions are not considered in the actual treatment exposure derivation

Note: In case the last days of cycle doses of ceralasertib are not taken (eg, Day 7) and no further medication will be taken, this is an interruption but will not be included in the total duration of dose interruptions as the total treatment exposure already includes this reduction via "date of last dose where dose > 0 mg".

The calculation of actual exposure makes no adjustment for any dose reductions that may have occurred.

Missed and forgotten doses should be recorded as a dose interruption with the reason recorded as "Patient forgot to take dose". These missed or forgotten doses are not included as dose interruptions in the summary tables, but the information appears in the listing for dosing. However, these missed and forgotten doses are considered in the derivation of actual exposure.

Dose intensity of study treatment(s) is addressed by considering relative dose intensity (RDI), where RDI is the percentage of the actual dose delivered relative to the intended dose through to treatment discontinuation. More specifically, RDI is defined as follows:

 $\circ$  RDI = 100% × d/D, where d is the actual cumulative dose delivered up to min(date of treatment discontinuation, date of death, data of DCO) and D is the intended cumulative dose up to the day of treatment discontinuation. D is the total dose that would be delivered, if there were no modification to dose or schedule.

Intended cumulative dose is calculated by summing the individual doses that should have been received up to and including the last day of study participation according to the planned dose and schedule.

This is given by the intended dose multiplied with the number of administrations that were planned to occur. These are different per treatment component.

- Intended cumulative dose of ceralasertib [mg] = daily dose × number of dosing days =•daily dose × [7 dosing days per number of complete cycles + dosing days of incomplete cycle]:
  - If  $mod_{28}(min(date of treatment discontinuation, date of DCO) date of first dose of ceralasertib + 1) ≤ 7 then:$

- Intended cumulative dose of ceralasertib = 240°mg × 2 × [7 × floor((min(date of treatment discontinuation, date of DCO) – date of first dose of ceralaserib +01)/28) + mod28(min(date of treatment discontinuation, date of DCO) – date of first dose of ceralasertib + 1)]
- Else if mod28(min(date of treatment discontinuation, date of DCO) date of first dose of ceralasertib + 1) > 7 then:
  - Intended cumulative dose of ceralasertib = 240 mg × 2 × [7 × floor(min(date of treatment discontinuation, date of DCO) – date of first dose of ceralasertib +o1)/28) + 7]
- Intended cumulative dose of durvalumab [mg] = dose × number of complete cycles = 1500°mg × ceil(min(date of treatment discontinuation, date of DCO) – date of first dose of durvalumab + 1)/28)

Note: ceil() refers to rounding up and floor() refers to rounding down to the next integer.  $mod_{28}(n)$  is the number n modulo 28.

Actual cumulative dose is calculated by summing all administered doses:

- ceralasertib dose = Actual dose recorded x actual frequency x duration
- durvalumab dose = Actual dose recorded

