#### **3.2.2** Study Treatment

The main study is a Phase 2, randomised, open-label, multicentre, international study assessing the efficacy and safety of ceralasertib and ceralasertib plus durvalumab in subjects with unresectable or advanced melanoma and primary or secondary resistance to programmed death-ligand 1 [PD-(L)1] inhibition. Approximately 150 subjects are randomised, at a 2:1 randomisation ratio (approximately 100 subjects in Arm 1 and approximately 50 subjects in Arm 2) to the following intervention groups:

- Arm 1: Ceralasertib 240 mg BD oral tablets, from Days 1 to 7 plus durvalumab 1500 mg Day 8, IV infusion, Q28D, until progressive disease, (confirmed RECIST 1.1-defined radiological progression), unacceptable toxicity, withdrawal of consent, or if a study treatment discontinuation criteria is met.
- 2. Arm 2: Ceralasertib 240 mg BD oral tablets, from Days 1 to 7, Q28D, until progressive disease, (confirmed RECIST 1.1-defined radiological progression), unacceptable toxicity, withdrawal of consent, or if a study treatment discontinuation criterion is met.

Crossover within the study is not be permitted. There is no defined maximum treatment duration for the treatment arms as the subjects receive study treatment until progressive disease (RECIST 1.1-defined radiological progression), unacceptable toxicity, withdrawal of consent, or if a study treatment discontinuation criterion is met.

Randomisation into the treatment arms is stratified by:

• Resistance to prior immune-oncology treatment (primary/early relapse in adjuvant setting vs secondary resistance).

• Baseline lactate dehydrogenase (LDH) expression (below and equal to the upper limit of normal vs above upper limit of normal).

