## 4.2.1.2 Presentation

Subject disposition including screen failures and reason for screen failure is summarised and listed based on all subjects screened by treatment arm and for all subjects combined as defined by the current relevant tables, figures, listings (TFL) standards. The number and percentage of subjects for the following are summarised if applicable:

- Subjects screened;
- Screen failures;
- Subjects randomised;
- Subjects randomised, did not receive study treatment
- Subjects started treatment
- Subjects who received ceralasertib and subjects who did not receive ceralasertib;
- Subjects who received durvalumab and subjects who did not receive durvalumab (for combination arm);
- Subjects ongoing study treatment at data cut-off;
- Subjects who discontinued treatment (including reason),
- Subjects ongoing study at data cut-off;
- Subjects who terminated study.

Summaries on disposition due to global/country situation due to a pandemic are added to the disposition table if applicable. The number and percentage of subjects for the following summaries are added on if applicable:

- Subjects who discontinued treatment due to global/country situation;
- Subjects who withdrew from study due to global/country situation.

The study disruptions due to the global/country situation is also summarised as a separate table.

The number and percentage of subjects with confirmed or suspected Coronavirus Disease 2019 (COVID-19) infection during the course of the study are presented separately, including details on COVID-19 related interruptions impacting on visits, and study drug administration. Discontinuation of study intervention and/or withdrawal from study due to COVID-19 are presented separately.

Listings of subjects affected by the COVID-19 pandemic are presented detailing any affect and impact on the study. Issues reported in the Clinical Trial Management System are considered for presentation in listings as well.

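### The durvalumab intended-dose formula starts at the infusion actually given first, so it does not compute the planned dose that the SAP itself defines as the denominator of relative dose intensity

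*SAP*

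**What the plan says.** Section 3.2.2 of the main-study SAP sets the combination regimen as ceralasertib on Days 1 to 7 "plus durvalumab 1500 mg Day 8, IV infusion, Q28D". With the first ceralasertib dose as Day 1, durvalumab is planned on Days 8, 36, 64 and so on.

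The RDI text in Section 4.3.12.1.1 sets RDI = 100% × d/D. It states that "D is the total dose that would be delivered, if there were no modification to dose or schedule", and it builds the intended dose from the administrations planned up to the subject's final day in the study. The durvalumab formula begins "Intended cumulative dose of durvalumab [mg] = dose × number of complete cycles" and continues as 1500 mg times the rounded-up number of 28-day intervals, with the clock starting at the actual first infusion: "date of first dose of durvalumab + 1)/28". The numerator adds up what was administered ("durvalumab dose = Actual dose recorded").

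The cut-off for d includes the date of death; the formulas for D use only treatment discontinuation and data cut-off.

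Section 4.3.14.1.1 of the sub-study SAP carries the same durvalumab formula, with exposure counted from Cycle 1 onwards.

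**The concern.** D is defined by the planned schedule, but the formula lets the denominator start whenever durvalumab happened to start. A first infusion that is omitted or postponed is a modification of the schedule, and the formula removes it from D. A missed later infusion stays in D. Two subjects with the same loss of drug can therefore receive different RDI values.

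A combination-arm subject who never received durvalumab has no first-infusion date, so the formula yields nothing, even where an infusion had fallen due. The SAP expects such subjects: the disposition table in Section 4.2.1.2 counts "Subjects who received durvalumab and subjects who did not receive durvalumab (for combination arm").

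At stake is whether the reported durvalumab dose intensity in the combination arm and the sub-study means what the SAP says it means.

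**Working it through.** The SAP states no numeric RDI, so there is no figure to reproduce. The check applies the formula as written and compares it with the SAP's own definition.

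**Inputs.** 1500 mg on Day 8 of each 28-day cycle (Section 3.2.2); D, d and the formula (Section 4.3.12.1.1). Day 1 is the first ceralasertib dose. Infusion days and stop days are illustrative assumptions.

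**Formulas.**
- As written: D = 1500 × ceil((stop − actual first infusion + 1)/28)
- As defined: D = 1500 × ceil((stop − 8 + 1)/28), and not below 0

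| Infusions given (days) | Stop day | d (mg) | D as written (mg) | RDI | D as defined (mg) | RDI |
|---|---|---|---|---|---|---|
| 8, 36, 64 (on time) | 84 | 4500 | ceil(77/28) = 3, 4500 | 100% | ceil(77/28) = 3, 4500 | 100% |
| 36, 64 (Cycle 1 omitted) | 85 | 3000 | ceil(50/28) = 2, 3000 | 100% | ceil(78/28) = 3, 4500 | 66.7% |
| 8, 64 (Cycle 2 omitted) | 85 | 3000 | ceil(78/28) = 3, 4500 | 66.7% | ceil(78/28) = 3, 4500 | 66.7% |
| 29, 57 (21 days late) | 84 | 3000 | ceil(56/28) = 2, 3000 | 100% | ceil(77/28) = 3, 4500 | 66.7% |
| 15, 43, 71 (7 days late) | 84 | 4500 | ceil(70/28) = 3, 4500 | 100% | ceil(77/28) = 3, 4500 | 100% |
| 15, 36, 64 (late, then realigned) | 70 | 4500 | ceil(56/28) = 2, 3000 | 150% | ceil(63/28) = 3, 4500 | 100% |
| none | 28 | 0 | no start date | no value | ceil(21/28) = 1, 1500 | 0% |

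**Omitted first infusion.** With 28-day spacing from Day 36, the defined RDI is 50.0% at stop Day 56, 66.7% at Day 84, 75.0% at Day 112 and 83.3% at Day 168. The formula as written gives 100% at each.

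**Late first infusion.** With 28-day spacing afterwards, the two versions differ only when treatment stops between a planned infusion day and the postponed one. That is the delay divided by 28 of all stop days: 7/28 = 25%, 14/28 = 50%, 21/28 = 75%, 28/28 = 100%. Over 12 whole intervals the enumerated shares agree. As written, the formula returned exactly 100% at every stop day tested, up to Day 336, for all four delays.

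**Realignment.** Section 3.2.5 allows later intervals to be shortened, so the 150% case is possible under the SAP.

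**Never given.** For a stop on Days 8 to 35, the defined D is 1500 mg and RDI is 0%. For a stop before Day 8, D = 0 and the absence of an RDI is correct.

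**Direction.** If the first infusion is not given before planned Day 8, a later start can only shrink D or leave it unchanged. The error therefore inflates RDI or has no effect.

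**The case against.** The strongest reply is that little depends on this figure and that the SAP reports the same failure elsewhere. A reader might infer that RDI is the only view of how much durvalumab was delivered. The SAP does not support that. Section 4.2.1.2 counts combination subjects who received no durvalumab. The actual-exposure rule subtracts Cycle 1 delay, measured from "the first administration of durvalumab on Day 8 and the first administration of ceralasertib on Day 1 is > 7 days". Section 4.3.12.1.2 summarises delays, reductions and interruptions with reasons, lists total drug received and adds exposure swimmer plots. This limits the consequence, not the error.

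A reader might also infer that any late first infusion is wrongly scored 100%. RDI counts whole infusions, so a short delay is often 100% on the planned schedule too, as the 7-day row shows.

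The SAP does not say that never-dosed subjects are excluded. What can be said is that the formula has no value for them and no rule assigns 0%, although the prose definition implies it.

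The Cycle 1 delay rule concerns a duration, not a cumulative dose, so its different anchor is not in itself a contradiction. The contradiction lies between the definition of D and its formula. The start date used for duration of exposure is likewise a separate quantity and no part of this point.

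Finally, counting from exactly Day 8 can be harsh. An infusion on Day 10 with a stop on Day 36 gives ceil(29/28) = 2 and 50%, where the present formula gives ceil(27/28) = 1 and 100%. That stands as a cost of the correction.

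**Conclusion.** The point holds as a mismatch between a definition and its formula, in both SAPs. An omitted first infusion is always dropped from D (100% instead of 66.7% in the Day 85 example). A late first infusion is dropped for a share of stop days that rises with the delay, and realignment can produce values above 100%. Where durvalumab was due and never given, the formula gives no value and the definition gives 0%.

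The result is an upward bias in one descriptive exposure summary. No efficacy analysis or interim rule in the SAP uses RDI, so nothing here bears on the efficacy conclusions. The per-subject sizes rest on assumed infusion and stop days, and the late-dose shares treat all stop days as equally likely. The number of subjects affected cannot be learned from the SAP, so the shift in the arm-level summary is unknown.

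**What to change.** In both SAPs, replace the durvalumab formula by:

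- D = 1500 mg × ceil((end date − (date of first ceralasertib dose + 7) + 1)/28), with D = 0 if the end date precedes the planned first infusion.
- In the sub-study, anchor on the first ceralasertib dose of Cycle 1, in line with its rule that Cycle 0 is not counted.
- Define the end date once and use the same cut-off for d and D, including how death is handled.
- Include every combination subject with D > 0, and set d = 0 where no durvalumab was given.

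This changes a reporting definition only and touches no dosing rule. It costs one formula and its programming in each SAP. Reported RDI becomes slightly less favourable, and a subject who stops on or just after a planned infusion day may be scored as missing that infusion; a table footnote can say so. Subjects dosed on schedule keep 100%.
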